#### **7.7.5 LOST TO FOLLOW-UP**

Subjects for which the final post-operative case report form is overdue and who refuse to be followed, or have difficulty being followed, or cannot be contacted despite extensive written and telephone follow-ups to determine the final clinical outcome, will be considered lost to follow-up. Sites must make a minimum of three documented attempts via telephone, email, or regular mail to contact the subject. If the subject does not reply to any of these attempts, the site must send a letter by certified mail (with a request for notification of receipt of delivery) to the subject. If a subject is non-responsive to these follow-up attempts, the subject will be considered to be lost to follow-up.

## 8 STATISTICAL METHODS

### 8.1 POPULATIONS FOR ANALYSIS

Exploratory effectiveness analyses will be performed on observed data for all primary eyes, fellow eyes, and all eyes successfully implanted with the RxLAL.

Safety analyses will be performed on observed data for all eyes of subjects who sign the informed consent and the procedure was attempted which is defined as the point at which the RxLAL makes contact with the eye. No imputation will be performed.

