### 5 OUTCOME PARAMETERS

#### 5.1 EXPLORATORY EFFECTIVENESS PARAMETERS

- Percent of eyes with UCDVA of 20/20 or better at 6 Months Postop (3 Months Post Lock-In)

Exploratory effectiveness analyses will be based on the 6-month UCDVA of eyes successfully implanted with the RxLAL.

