#### 7.4 EXAMINATION SCHEDULE

Subjects who agree to participate in the study will return for the listed follow-up examinations for each study eye:

Evaluation	
Preoperative	Day -90 to Day -1
Operative	Day 0, day of surgery
Postop Day 1	Days 1 to 2 postop
Postop Week 1	Days 7 to 14 postop
Postop Week 3	Days 17 to 24 postop: Adjustment #1
Adjustment #2, if needed	3 to 7 days post Adjustment #1
Adjustment #3, if needed	3 to 7 days post Adjustment #2
Lock-in #1	3 to 7 days post final adjustment
Lock-in #2, if needed	3 to 7 days post lock-in #1
Post Lock-In	3 to 7 days post final lock-in
1 Month Post Lock-In	30 to 60 days post final lock-in
3 Months Post Lock-In/6 Months Postop	Days 120 to 180 postop

Unscheduled visits falling outside the designated ranges for scheduled visits will be considered “interim” visits for data recording purposes and a report form will be completed.

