## 7.7 STUDY COMPLETION PROCEDURES

An End of Study Form must be completed for all subjects enrolled in the study upon subject completion, withdrawal or discontinuation.

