#### **7.7.4 SUBJECT DISCONTINUATION AFTER IMPLANTATION**

After implantation, subjects may not be withdrawn from the study unless the study lens has been explanted. In the case of an explant, the investigator should continue follow-up for a period that ensures no adverse consequences have resulted. When possible, all necessary clinical assessments will be performed prior to the Subject exiting the study even if the assessment was not scheduled at that particular visit.

Subjects may be discontinued from the study only when the study lens has been explanted or subject has deceased. The reason for discontinuation will be recorded on the appropriate study worksheet. Subjects who are discontinued from the study will still be a part of the study analyses up until the point they are exited.

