##### UCDVA

Number and percent of primary eyes, fellow eyes, and all eyes (i.e. primary and fellow eyes) successfully implanted with the RxLAL with a UCDVA of 20/20 or better at 6 Months Postop (3 Months Post Lock-In) will be presented and the corresponding 95% confidence interval for the percent based on the binomial distribution will be calculated.

UCDVA will be presented with the number and percent of eyes that fall into each category of UCDVA (e.g. 20/20 or better, 20/25 or better, 20/32 or better, etc.) at each visit. The mean UCDVA letter score will be calculated for each visit. Change in UCDVA from Postop Week 3 will be presented at each visit as categorical outcomes of “increase in 15 letters or more”, “Increase in 10-14 letters”, “Increase in 5-9 letters”, “No change”, “Decrease in 5-9 letters”, “Decrease in 10-14 letters”, and “Decrease in 15 letters or more”. The mean change from Postop Week 3 will also be presented.

UCDVA will also be presented with the number and percent of eyes that fall into each category of UCDVA (e.g. 20/20 or better, 20/25 or better, 20/32 or better, etc.) stratified into two bins based on preoperative keratometric cylinder ( $\geq 0.50$  D and  $\leq 1.50$  D) and ( $> 1.50$  D and  $\leq 3.00$  D). The mean UCDVA letter score will be calculated for each of the two defined preoperative keratometric cylinder bins.

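### An eye whose RxLAL is explanted drops out of the observed-only 20/20 percent if the subject exits before the 6-month visit, which tends to raise the percent slightly

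*Combined protocol and SAP*

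**What the plan says.** Section 5.1 lists one effectiveness parameter, the percent of eyes with UCDVA of 20/20 or better at 6 months, and adds: "Exploratory effectiveness analyses will be based on the 6-month UCDVA of eyes successfully implanted with the RxLAL". Section 8.1 sets the population and the handling of missing values together: "Exploratory effectiveness analyses will be performed on observed data for all primary eyes, fellow eyes, and all eyes successfully implanted with the RxLAL". Under the UCDVA heading of Section 8.1.1, the number and percent of eyes "successfully implanted with the RxLAL with a UCDVA of 20/20 or better at 6 Months Postop (3 Months Post Lock-In) will be presented", with a 95% binomial confidence interval, for primary eyes, fellow eyes and all eyes. The plan does not define successful implantation, and it does not require the RxLAL to be still in the eye when the 6-month reading is taken.

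Section 7.7.4 permits discontinuation after implantation only for explant or death. Discontinued subjects "will still be a part of the study analyses up until the point they are exited". After an explant, "the investigator should continue follow-up for a period that ensures no adverse consequences have resulted"; no length is given for that period. The 6-month visit has the window "Days 120 to 180 postop" in Section 7.4.

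Explants are recorded. Section 7.7 requires: "An End of Study Form must be completed for all subjects enrolled in the study upon subject completion, withdrawal or discontinuation". Section 7.7.4 adds: "The reason for discontinuation will be recorded on the appropriate study worksheet". Section 9.2.3 calls for expedited reporting of an explant from a study eye, and Section 8.2 presents all secondary surgical interventions.

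**The concern.** An analysis of observed data is neutral only if the eyes without a 6-month value resemble those with one. Explanted eyes may well not. Section 9.2.5 names vision made worse by adjustment or lock-in as a reason to remove and replace the lens, and a pupil that cannot be dilated enough for treatment as a reason to explant. Had they kept the lens, many of these eyes would probably not have reached 20/20. If they leave the denominator, the percent describes the eyes in which the lens stayed, while a reader may take it to describe all eyes implanted.

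A second matter is open. If the subject is followed to the 6-month visit with a replacement lens, the visible text does not say how that reading counts. Without a rule, the choice would be made after the data are known.

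**Working it through.** **No stated figure to reproduce.** The documents give no expected 20/20 rate, explant rate, dropout rate or sample-size calculation for this study. The counts below are assumptions chosen to show scale.

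**Inputs.**
- N = 150 eyes in 75 subjects, so 75 primary eyes: the maximum in Section 6.
- Observed rate r = 88%: the rate cited in Section 2.1 from an earlier study of the lens. It is used only as an illustration and is not a planning value for this trial. The range 80% to 95% is also shown.
- k = explanted eyes that drop out, assumed 1 to 3 among 150 eyes.

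**Step 1: what the rules do.** Observed data only (8.1, 8.1.1) combined with analysis only until exit (7.7.4) means that exit before day 120 leaves no 6-month value. Section 7.7.4 asks for assessments before exit where possible, but Section 7.4 classes an unscheduled visit outside the windows as interim, so an early exit examination does not supply the endpoint.

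**Step 2: shift when only the explanted eyes drop out.** With r observed among N − k eyes, counting the k eyes as not 20/20 gives r(N − k)/N. The difference is r − r(N − k)/N = r·k/N.

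| N | k | Shift at 88% (points) | Shift at 80% to 95% (points) |
|---|---|---|---|
| 150 | 1 | 0.88 × 1/150 = 0.59 | 0.53 to 0.63 |
| 150 | 3 | 0.88 × 3/150 = 1.76 | 1.60 to 1.90 |
| 75 | 1 | 0.88 × 1/75 = 1.17 | 1.07 to 1.27 |
| 75 | 2 | 0.88 × 2/75 = 2.35 | 2.13 to 2.53 |

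In whole eyes, with three explants among 150: 129/147 = 87.8% observed-only, against 129/150 = 86.0% with explants as not 20/20. For primary eyes k is taken as 1 to 2, because three explants among all eyes would not usually all fall in primary eyes.

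**Step 3: the other eye of a bilateral subject.** Section 7.7.4 discontinues the subject, not the eye, so the other eye may be lost as well. With three such subjects, 150 − 6 = 144 eyes are observed.
- If the three other eyes would all have been 20/20: (129 − 3)/144 = 126/144 = 87.5%.
- If none would have been: 129/144 = 89.6%.

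Against 86.0%, the shift is 1.5 to 3.6 points.

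**Step 4: comparison with sampling error.** Exact (Clopper-Pearson) 95% intervals, treating paired eyes as independent:
- 129/150: 79.4% to 91.1%, half-width about 5.9 points.
- 129/147: 81.3% to 92.6%, about 5.6.
- 126/144: 81.0% to 92.4%, about 5.7.
- 129/144: 83.4% to 94.1%, about 5.3.
- Primary eyes, 65/74 (one explant): 78.2% to 94.3%, about 8.1.
- Primary eyes, 64/73 (two explants): 77.9% to 94.2%, about 8.2.

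Every shift in Steps 2 and 3 is smaller than the half-width. With k = 0 the shift is zero.

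**The case against.** The plan openly declares a descriptive analysis of observed data in an exploratory study with no primary effectiveness endpoint, and no test or threshold depends on the percent. Secondary interventions are presented under safety and the number of eyes is shown with the percent, so a reader could roughly bound the effect of eyes that drop out. All of this stands, and it limits the severity. It does not restore the lost eyes to the percent.

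Three stronger readings are tempting, and the documents do not support them.

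- *A reader might infer that a 20/20 reading through a replacement lens will be counted as an RxLAL success.* No rule says so. Sections 1 and 3 set the objective as vision after lock-in of the implanted RxLAL. Section 7.3.1 bars additional refractive procedures before the 6-month visit, and Section 2 lists IOL exchange among procedures for residual refractive error. Follow-up after explant in 7.7.4 has a safety purpose and no stated length, so it may not reach the visit. The contents of Table 2 and the assessment reference are not visible. No visible passage is a counting rule in either direction, so this is an ambiguity.
- *A reader might treat every explant as a device failure.* Section 9.2.5 also names a lens scratched or badly placed when surgical procedures are not followed. The link to failure is therefore partial, and counting all explants as not 20/20 is one reasonable convention, best shown as a supplement.
- *A reader might apply three explants to the 75 primary eyes as well.* That doubles the assumed explant rate from 3/150 = 2% to 3/75 = 4% and inflates the primary-eye shift.

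The direction is also a tendency. An explanted eye that is followed and reads worse than 20/20 is already a non-success and causes no overstatement.

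**Conclusion.** The concern holds for explanted eyes whose subjects exit before the 6-month visit: applying the plan exactly removes them from the only listed effectiveness percent. Because explant is partly tied to worsened vision or undeliverable treatment, the loss plausibly favors the lens. For subjects who are followed to the visit with a replacement lens, the plan is silent.

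At an assumed 88% observed rate, three explants among 150 eyes raise the percent by about 1.8 points, and one to two of them among 75 primary eyes raise it by about 1.2 to 2.3 points. If bilateral subjects' other eyes leave too, the all-eyes shift is 1.5 to 3.6 points. These figures rest on assumed explant counts, on all explanted eyes exiting early, and on no other missing eyes. The effect is on how a descriptive percent is read, so the severity is minor and the change is a cheap improvement.

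**What to change.** In Section 8.1.1, under UCDVA:

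1. Keep the observed-only percent. Beside it, add a supplementary percent in which every eye implanted with the RxLAL and explanted before the 6-month visit stays in the denominator as not 20/20, whether or not a reading through a replacement lens exists.
2. State that readings taken through a replacement lens are left out of the observed-only percent, and say that this modifies the planned rule. Such eyes then drop out of that percent, and the supplementary percent shows the effect.
3. Next to both, give the number of eyes explanted, the number of fellow eyes lost because the subject exited after the other eye was explanted, and the number otherwise missing at 6 months. The second count is needed because the supplementary percent does not recover those eyes. In the Step 3 example it would be 126/147 = 85.7% or 129/147 = 87.8%.

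The cost is a few sentences and one extra table line, from data that are already collected. The downside is a possibly slightly lower reported percent.

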### 4 STUDY DESIGN

A prospective, single center, randomized, exploratory clinical study will be conducted. Subjects will be followed for a 6-month period.

Patients who require cataract extraction and intraocular lens implantation will be screened for eligibility. If it is determined that the patient may be eligible to participate, study staff will explain the study purpose, procedures, risks/benefits and subject responsibilities to the potential participant. Written informed consent will be obtained prior to any study specific testing. The patient is enrolled upon signing the informed consent. If both eyes of a patient meet study eligibility, a pre-determined randomization scheme will be utilized to designate each of the patient's eyes as the primary eye or the fellow eye. If only one eye of a patient meets study eligibility, that eye will automatically be designated as the primary eye.

At 3 weeks post-implantation, eyes will be refracted, undergo visual testing, and receive a power adjustment based on the manifest refraction. Subjects will return 3 to 7 days after their adjustment and the same measurements performed again. Depending on the adjustment(s) performed, subjects will receive one to three adjustments and one or two lock-in treatments.

Postoperatively, subjects will undergo complete ophthalmic examinations at regular intervals over a 6-month period.

Uncorrected distance visual acuity (UCDVA) and responses from the Quality of Vision (QoV) questionnaire will be summarized. All ocular adverse events (device related and unrelated) during the conduct of the study will be reported. All Secondary Surgical Interventions (SSIs) in study eyes during the conduct of the study will also be reported.

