#### 5.2 SAFETY PARAMETERS

The following safety parameters will be evaluated at 6 Months Postop (3 Months Post Lock-In):

- Ocular adverse events (device related and unrelated) of the study eyes during the conduct of the study.
- Secondary Surgical Interventions (SSIs) of the study eyes during the conduct of the study.

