## 6 STUDY POPULATION

The study population will consist of up to 150 eyes in up to 75 subjects with 0.50 to 3.00 D of pre-operative keratometric astigmatism implanted with the RxLAL. Approximately 1/2 of the study population should have  $\geq 0.50$  D and  $\leq 1.5$  D of preoperative keratometric astigmatism and approximately 1/2 of the study population should have  $> 1.5$  D and  $\leq 3.00$  D of preoperative keratometric astigmatism. At least 10 eyes should have  $> 2$  D of preoperative keratometric astigmatism.

Both eyes of all subjects should be screened for eligibility.

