### 6.1 INCLUSION CRITERIA

- Must sign a written Informed Consent form and be willing to undergo cataract surgery for unilateral or bilateral implantation of the RxLAL.
- Between the ages of 40 and 80 inclusive on the day the cataract surgery is performed.
- Study eye must have preoperative keratometric cylinder of  $\geq 0.50$  D and  $\leq 3.00$  D.
- Study eye must have cataract causing reduction in best corrected distance visual acuity (BCDVA) to a level of 20/32 or worse with or without a glare source.
- Study eye must have best corrected distance visual acuity projected (by clinical estimate based upon past ocular history or retinal exam) to be 20/20 or better after cataract removal and IOL implantation.
- If only one subject eye is enrolled in the study, the non-study eye must have potential for BCDVA of 20/40 or better after cataract removal and IOL implantation.
- Study eye has clear intraocular media other than cataract.
- Willing and able to comply with the requirements for study specific procedures and visits.
- Study eye has a dilated pupil diameter of  $\geq 7.0$  mm.
- Study eye requires an IOL power within the range available for the RxLAL.

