### **7.3 RXLAL IMPLANTATION AND REFRACTIVE ADJUSTMENT**

#### **7.3.1 SURGICAL PROCEDURE**

The RxLAL will be implanted on Day 0 of the study using standard microsurgical techniques.

No additional refractive procedures are allowed until after the 3 Month Post Lock-In/6 months postop visit.

In subjects with both eyes enrolled, if surgical complications occur with the primary eye and no RxLAL is implanted, the subject should be Exited from the study and no RxLAL should be implanted in the fellow eye.

The surgical procedure will be performed as follows:

1. Prepare and drape the eye for surgery in accordance with standard surgical procedures.
2. A temporal clear corneal incision will be made at a location of the surgeon's discretion using the surgeon's standard instrumentation and techniques.
3. Use viscoelastic to fill the anterior chamber through the incision opening.
4. Perform an anterior circular capsulorhexis of a maximum of 5.2 mm in diameter using standard technique. The capsulorhexis should be well-centered with a 360° overlapping capsular edge to minimize IOL tilt and decentration and longitudinal IOL shift. The capsulorhexis and/or nuclear fragmentation can be performed with a femtosecond laser. Precision pulse capsulotomy (PPC) can also be used to perform the capsulorhexis.
5. The surgeon will extract the cataract by phacoemulsification.
6. In the event of an intraoperative complication prior to implantation of the RxLAL, including posterior capsule rupture, zonular rupture, radial capsulorhexis tear, vitreous loss, iris trauma, corneal complications or any intraoperative abnormality that may affect the postoperative pupillary dilation, or the centration or tilt of the intraocular lens, do not implant the RxLAL.
7. The RxLAL can be introduced into the eye using any of the following insertion systems:
  - a. The RxSight Insertion Device through a clear temporal corneal incision up to 3.2 mm
  - b. Nichamin III Foldable Lens Inserter (Rhein Medical 05-2349) with the Nichamin II Foldable Lens Insertion Forceps (Rhein Medical 05-2348) through a temporal clear corneal incision of 3.5-3.8 mm.
  - c. An insertion system of the investigator's choice.

The RxLAL is placed into the capsular bag. If utilizing additional surgical instruments near the incision upon insertion, precaution should be taken not to contact the RxLAL optic with this additional instrument.

8. Verify proper orientation of the RxLAL

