## 8.2 SAFETY PARAMETERS

All ocular adverse events (device related and unrelated) and all Secondary Surgical Interventions (SSIs) of the study eyes during the conduct of the study will be presented.

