### 8.2.1 ADDITIONAL SAFETY ANALYSES

The safety outcomes will be summarized descriptively for all eyes that have the procedure attempted.

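### Does the lens-contact rule for the safety population wrongly drop adverse events in eyes whose surgery stopped before the RxLAL was introduced?

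*Combined protocol and SAP*

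**What the plan says.** Section 8.1 defines the safety population as eyes of consented subjects in which "the procedure was attempted which is defined as the point at which the RxLAL makes contact with the eye". Section 8.2.1 repeats the condition: "The safety outcomes will be summarized descriptively for all eyes that have the procedure attempted".

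Three other places describe adverse event output without mentioning lens contact:

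- Section 4: "All ocular adverse events (device related and unrelated) during the conduct of the study will be reported".
- Section 5.2 lists, as a safety parameter, "Ocular adverse events (device related and unrelated) of the study eyes during the conduct of the study".
- Section 8.2 commits to presenting "All ocular adverse events (device related and unrelated) and all Secondary Surgical Interventions (SSIs) of the study eyes during the conduct of the study".

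The protocol foresees eyes that never reach lens contact. Step 6 of Section 7.3.1 begins "In the event of an intraoperative complication prior to implantation of the RxLAL" and directs that the lens then not be implanted. Section 7.7.3 has such subjects followed until their adverse events resolve, after which they leave the study.

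**The concern.** Read literally, the sections give two scopes for one output. A posterior capsule rupture during phacoemulsification, before the lens is introduced, is an ocular adverse event during the study, so Sections 4 and 8.2 appear to include it. Section 8.1 excludes the eye. No sentence says which text prevails, and two analysts could produce different adverse event listings.

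The omission would also be selective, because the eyes left out are out precisely because of an intraoperative complication. If both eyes of a subject are enrolled and the primary eye is stopped, Section 7.3.1 exits the subject and bars the lens from the fellow eye, so that subject is absent from the safety results altogether. At stake is the completeness of the reported adverse events.

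**Working it through.** The plan gives no figure to reproduce, so most of the check is a comparison of texts.

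**1. Which eyes are affected**

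| Eye | Section 8.1 | Wording of Sections 4 and 8.2 |
|---|---|---|
| RxLAL contacted the eye, implanted or not | in, including its earlier events | in |
| Primary eye stopped before contact | out | in |
| Fellow eye stopped before contact, primary eye contacted | out if the condition applies by eye; possibly in if it applies by subject | in |
| Enrolled at consent, never operated | out, unless the subject's other eye was contacted and the condition is read by subject | in under Section 4; under 8.2 if it counts as a study eye |

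For the third row, Section 8.2.1 is worded by eye, which supports the by-eye reading.

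**2. How the sections relate**

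- Section 8.1 is headed as the populations section and covers safety analyses without exception. Section 8.2 names the outcomes. It need not restate the population and does not claim to override it.
- Section 8.2.1 speaks of the safety outcomes in general and repeats the contact condition.
- Section 5.2 does not say that all events are covered, and it ties evaluation to the visit 3 months after lock-in, which an unimplanted eye cannot have.
- Section 6 describes the study population as "up to 150 eyes in up to 75 subjects with 0.50 to 3.00 D of pre-operative keratometric astigmatism implanted with the RxLAL". The title of Table 2 is likewise limited to implanted eyes.
- Section 7.7.4 keeps subjects discontinued after implantation in the analyses up to their exit. Section 7.7.3, for stops before implantation, has no such sentence. The contrast fits a deliberate exclusion.
- Pointing the other way, Section 6.1 applies the term to eyes before surgery ("Study eye must have preoperative keratometric cylinder of"), and the adverse event sentence in Section 4 is not limited to study eyes.

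On balance Section 8.1 governs the analyses. Section 4 is the one text clearly wider, and it speaks of reporting, which a listing satisfies.

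**3. What would change in the results**

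- Effectiveness: nothing, because those analyses use successfully implanted eyes.
- BCDVA, IOP, slit lamp and fundus summaries: nothing, because Section 8.2.1 puts them on the contact set.
- Adverse events and SSIs: Section 8.2 specifies no denominator, percentage or interval. The confidence interval in Section 8 is for UCDVA. The only effect is whether some events appear in a listing.

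**4. How many eyes**

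The documents give no rate of stops before lens contact. Let r be an assumed share of operated primary eyes that are stopped, and n the number of implanted primary eyes (one per subject; Sections 6 and 7.2 give up to, or about, 75 subjects).

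- Expected stopped eyes = n × r / (1 − r)
- P(at least one) = 1 − (1 − r)^n

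| r (assumed) | Expected, n = 75 | P, n = 75 | P, n = 60 |
|---|---|---|---|
| 0.5% | 0.38 | 31% | 26% |
| 1% | 0.76 | 53% | 45% |
| 2% | 1.53 | 78% | 70% |
| 3% | 2.32 | 90% | 84% |

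For example, at r = 0.5% and n = 75, 0.995^75 = 0.687, so no stopped eye is the likelier outcome. The column n = 60 is an assumed smaller study. Stopped fellow eyes are not counted.

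**5. Whether the information is lost**

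Section 9.2.1 starts adverse event collection at consent. Section 7.7.3 follows these subjects to resolution. Section 9.2.3 sends serious events to the sponsor and the Ethics Committee. The data exist whichever reading is taken.

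**The case for a change.** The strongest case for a change is that the reading in step 2 is an inference. Section 8.2.1 is headed as additional analyses, so its condition may not reach the main adverse event presentation. Section 8.2 omits a condition that its neighbour states, and Section 4 lies outside Section 8. Omitting eyes because they had a complication is not random, and settling the matter before results are known would cost a sentence or two and a listing that may be empty.

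Part of this stands. The plan does not say where adverse events of uncontacted eyes appear, and the omission would be selective. But these eyes received neither lens nor light treatment, so pooling them into device-safety results would blur those results. Even the proposed remedy keeps the contact set for every table and rate and adds only a separate listing. Section 8.1 does not forbid that listing, and Section 4 is enough reason to provide it. A remedy limited to eyes whose surgery had begun would also leave out events in enrolled eyes never operated on, so it would not fully match Section 4.

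**Conclusion.** No change to the plan follows. The sections differ in wording, but they work together: Section 8.1 defines who is analysed, Section 8.2 names what is shown, and the broader promise in Section 4 can be met by a listing beside the main tables. The contact-based set suits a device study and is wider than the effectiveness set, since it keeps eyes the lens touched but in which implantation failed.

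Under assumed stop rates of 0.5% to 3%, about 0.4 to 2.3 primary eyes would be involved per 75 implanted. The study is exploratory and descriptive, with no primary effectiveness endpoint, and no specified estimate or device-safety conclusion moves.

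This rests on two assumptions: that Section 8.1 governs Section 8.2, which is the natural reading though not an explicit one, and that events collected under Section 9.2.1 remain available to whoever writes the report. What remains is a gap in detail that analysts can fill without an amendment.
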